9.4.6 Hepatic Monitoring

If a subject experiences elevated alanine aminotransferase (ALT) or aspartate aminotransferase (AST) $\geq 3 \times$ upper limit of normal (ULN), alkaline phosphatase (ALP) $\geq 2 \times$ ULN, or elevated total bilirubin (TBL) $\geq 2 \times$ ULN, liver tests will be performed to confirm the abnormality. Additional safety data may be collected if required, as defined in the protocol. Where applicable, the following will be presented.

The subjects' liver disease history and associated person liver disease history data will be listed. Any concomitant medications that have potential for hepatotoxicity, including acetaminophen will be listed. Results from any hepatic monitoring procedures, such as a magnetic resonance elastography (MRE) scan, and biopsy assessments will be listed, if performed.

Hepatic risk factor assessment data will be listed. Liver related signs and symptoms data will be summarized by treatment and listed. Alcohol and recreational drug use data will also be listed.

All hepatic chemistry, hematology, coagulation, and serology data will be listed. Values outside the reference ranges will be flagged on the individual subject data listings.

9.4.7 Hypersensitivity reactions

For all drug hypersensitivity reactions that occur, additional follow-up data will be collected to assess the patient's medical history, alternative causes, and symptoms.

These data will be listed.

9.4.8 Infusion-site reactions

Infusion-site reaction data will be listed and summarized by treatment in frequency tables.

The severity of all ISRs will be assessed using the Division of Allergy and Infectious Diseases (DAIDS) Table for Grading the Severity of Adult and Pediatric Adverse Events, version 2.1 (July 2017).

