6.1.1.2. Management of Infusion Reactions

All participants should be monitored closely, during and after infusion as specified in the SoA, as there is a risk of infusion reaction and hypersensitivity (including anaphylaxis) with any biological agent.

Symptoms and Signs

Symptoms and signs that may occur as part of an infusion reaction include, but are not limited to fever, chills, nausea, headache, bronchospasm, hypotension, angioedema, throat irritation, rash including urticaria, pruritus, myalgia, and dizziness.

Severity of infusion-related reactions will be assessed and reported using the Division of Allergy and Infectious Diseases (DAIDS) Table for Grading the Severity of Adult and Pediatric Adverse Events, version 2.1 (July 2017).

This table describes the severity of reactions according to DAIDS.

Parameter	Mild	Moderate	Severe	Severe and Potentially Life-threatening
Acute Allergic Reaction	Localized urticaria (wheals) with no medical intervention indicated	Localized urticaria with intervention indicated OR Mild angioedema with no intervention indicated	Generalized urticaria OR Angioedema with intervention indicated OR Symptoms of mild bronchospasm	Acute anaphylaxis OR Life-threatening bronchospasm OR Laryngeal edema
Cytokine Release Syndrome ^a	Mild signs and symptoms AND Therapy, that is, antibody infusion interruption not indicated	Therapy indicated (that is, antibody infusion) interruption indicated AND Responds promptly to symptomatic treatment OR Prophylactic medications indicated for ≤ 24 hours	Prolonged severe signs and symptoms OR Recurrence of symptoms following initial improvement	Life-threatening consequences (for example, requiring pressor or ventilator support)

^a A disorder characterized by nausea, headache, tachycardia, hypotension, rash, and/or shortness of breath.

Source: Division of AIDS (DAIDS) Table for Grading the Severity of Adult and Pediatric Adverse Events, Version 2.1 (July 2017).

Site Needs

The site must have resuscitation equipment, emergency drugs (including but not limited to oxygen, IV fluid, epinephrine, acetaminophen, and antihistamine) and appropriately trained personnel available during the infusion and for at least 6 hours after the completion of the infusion.

Management of Infusion Reactions

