8.3.6. Hypersensitivity Reactions

Many drugs, but particularly biologic agents, carry the risk of systemic hypersensitivity reactions. If such a reaction occurs, additional details describing each symptom should be provided to the sponsor in the infusion-related reaction/hypersensitivity CRF.

If symptoms and/or signs occur during or within 6 hours after end of infusion of LY3832479 and are believed to be hypersensitivity or due to cytokine release, then investigators are encouraged to report the event as infusion-related immediate hypersensitivity reaction or cytokine release-associated infusion reaction, respectively.

Sites should have appropriately trained medical personnel and appropriate medical equipment available when study participants are receiving intervention. It is recommended that participants who experience a systemic hypersensitivity reaction be treated per national and international guidance (Lieberman et al 2015; Simons et al. 2015)

In the case of generalized urticaria or anaphylaxis, additional blood and urine samples should be collected as described in Section 10.7, Appendix 7, "Recommended Laboratory Testing for Hypersensitivity Events". Laboratory results are provided to the sponsor via the central laboratory.

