8.3.8. Infusion-Related Reactions

As with other mAbs, infusion-related reactions may occur during or following LY3832479 administration. If an infusion-related reaction occurs, additional data describing each symptom and sign should be provided to the sponsor in the CRF.

This table describes the location of infusion-related reaction information in this protocol.

Topic	Location
Special treatment considerations	Section 6.1.1
Management of infusion reactions	Section 6.1.1.2
DAIDS table describing severity	Section 6.1.1.2
Treatment guidelines for infusion-related reactions	Section 6.1.1.2

Symptoms occurring during or after infusion of study intervention may also be defined according to AE categories such as acute allergic reaction or cytokine release syndrome (refer to DAIDS).

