2. ABBREVIATIONS

Abbreviations pertain to the Statistical Analysis Plan (SAP) only (not the tables, figures and listings [TFLs]).

AE	Adverse event
ALP	Alkaline phosphatase
ALT	Alanine aminotransferase
AST	Aspartate aminotransferase
AUC	Area under the concentration versus time curve
AUC(0-∞)	Area under the concentration versus time curve from time zero to infinity
AUC(0-t _{last})	Area under the concentration versus time curve from time zero to time t, where t is the last time point with a measurable concentration
%AUC(t _{last} -∞)	Percentage of AUC(0-∞) extrapolated
BQL	Below the lower limit of quantification
CL	Total body clearance of drug calculated
C _{max}	Maximum observed drug concentration
CRF	Case Report Form
CRU	Clinical Research Unit
CSR	Clinical Study Report
CV	Coefficient of variation
DAIDS	Division of Allergy and Infectious Diseases
ECG	Electrocardiogram
ICF	Informed consent form
ICH	International Conference on Harmonisation
IV	Intravenous
MedDRA	Medical Dictionary for Regulatory Activities
MRE	Magnetic resonance elastography
PK	Pharmacokinetic
SAP	Statistical Analysis Plan
SARS-CoV-2	Severe acute respiratory syndrome coronavirus 2
SD	Standard deviation
TFLs	Tables, Figures, and Listings

$t_{1/2}$	Half-life associated with the terminal rate constant (λ_z) in non-compartmental analysis
TBL	Total bilirubin
t_{last}	Time of the last observed drug concentration
t_{max}	Time of maximum observed drug concentration
ULN	Upper limit of normal
V_{ss}	Volume of distribution at steady state
V_z	Volume of distribution during the terminal phase
WHO	World Health Organization

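### SAP 9.4.8 tabulates and DAIDS-grades infusion-site reactions, whereas the protocol grades and collects infusion-related reactions; probably a mislabel, but it needs correcting

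*SAP*

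**What the plan says.** SAP 9.4.8 is headed for infusion-site reactions. It plans a listing and a table: "Infusion-site reaction data will be listed and summarized by treatment in frequency tables". It then sets the grading: "The severity of all ISRs will be assessed using the Division of Allergy and Infectious Diseases (DAIDS) Table", version 2.1 of July 2017. The SAP does not expand ISR in that section or in its abbreviation list (section 2), and it does not say what counts as an infusion-site reaction.

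Protocol 6.1.1.2 uses the same table and version for another event: "Severity of infusion-related reactions will be assessed and reported using the Division of Allergy and Infectious Diseases (DAIDS) Table". Its non-exhaustive list of signs reads "fever, chills, nausea, headache, bronchospasm, hypotension, angioedema, throat irritation, rash including urticaria, pruritus, myalgia, and dizziness". Protocol 8.3.8 asks for detail on these events: "If an infusion-related reaction occurs, additional data describing each symptom and sign should be provided to the sponsor in the CRF". Protocol 8.3.6, on hypersensitivity, names the form: "additional details describing each symptom should be provided to the sponsor in the infusion-related reaction/hypersensitivity CRF".

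**The concern.** A reaction at the infusion site and an infusion-related reaction are different events. The first is local. The second, as the protocol describes it, can involve fever, hypotension or bronchospasm and is not defined by location. The SAP therefore attaches its dedicated frequency table and its only DAIDS grading to an event for which the protocol names no form or assessment. It does not mention the event that the protocol does grade and collect.

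Safety and tolerability are the primary objective, and a severe acute infusion reaction is the first theoretical risk listed in protocol 2.3. Under SAP section 3, the SAP and the table shells become the template for the study report, so whoever programmes the tables works from this wording. On a literal reading the site-reaction table could be empty. SAP 13.3 would then print a no-data message, which a reader could mistake for the absence of infusion reactions.

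**Working it through.** The documents give no figure to reproduce, so the check compares the sections.

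**1. The terms in the supplied text**

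| Term | SAP | Protocol |
|---|---|---|
| infusion-site | 3 (contents list, heading, one sentence) | 0 |
| infusion-related | 0 | used in 6.1.1.2, 8.3.6 and 8.3.8, among others |
| ISR expanded or defined | no | not applicable |

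**2. Grading instrument.** Both documents cite DAIDS version 2.1 (July 2017). The instrument matches and only the event differs. This points to a label error more than to a deliberate change.

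**3. The protocol's event.**
- Protocol 6.1.1.2 gives 12 example signs, and none is described as being at the infusion site.
- It reproduces 2 DAIDS rows, acute allergic reaction and cytokine release syndrome. Protocol 8.3.8 names the same 2 categories.
- Protocol 8.3.6 offers 2 reporting terms: "investigators are encouraged to report the event as infusion-related immediate hypersensitivity reaction or cytokine release-associated infusion reaction". Neither is a site reaction.

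**4. Whether another SAP section covers infusion-related reactions.**
- SAP 9.1 restricts summaries to data for which the SAP specifies them.
- SAP 9.4.7 only lists the follow-up data on hypersensitivity reactions. It plans no table and no DAIDS grade.
- SAP 9.4.10 leaves any safety assessment not covered in that section as a listing.
- SAP 9.4.1 tabulates treatment-emergent events by treatment, severity, relationship, system organ class and preferred term. Reactions recorded as such events are counted there. Symptoms coded under separate terms would not, however, give one count of participants with any infusion-related reaction. The general intensity scale in protocol 10.3.3 has 3 levels, whereas the DAIDS extract in 6.1.1.2 has 4.

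Read literally, then, the data on the infusion-related reaction form are listed, and no dedicated by-treatment, DAIDS-graded summary of them is planned.

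**5. Whether the change is declared.** SAP section 3 says that substantial differences from the protocol will be identified. Section 11 reports none. The change of event is either a slip or undeclared.

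**The case against.** The best defence is that 9.4.8 already is the infusion-related reaction table under a loose label. The DAIDS citation is identical. SAP 9.4.7 to 9.4.9 cover hypersensitivity, infusion reactions and SARS-CoV-2 infection, the same topics as protocol 8.3.6 to 8.3.8. The protocol names only one form for such events. The table shells, which may carry the right title, are not supplied, so no missing table can be shown. This stands as the likely explanation. It does not remove the need for a correction, because the written rule still names another event.

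The evidence on event type also has limits. The list of signs is open-ended, rash and pruritus carry no location, and the DAIDS extract grades localized urticaria. The full DAIDS table is not supplied, so its criteria for site reactions cannot be checked. Localized does not mean at the infusion site, though, and the protocol never makes that link.

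A reader might infer that infusion-reaction data would be lost. The documents do not support this. Protocol 8.3.1 collects all adverse events, SAP 9.4.1 lists them and tabulates those that are treatment-emergent, and serious events are listed. With at most 30 participants, individual reactions can be found in the listings. A reader might also infer that a form dedicated to infusion-related reactions goes unused. The form is shared with hypersensitivity, and SAP 9.4.7 already lists hypersensitivity follow-up data. Finally, protocol 9.4.2 does not promise a table by DAIDS grade; that table is the SAP's own plan.

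**Conclusion.** The point holds as a wording error in a stated analysis rule. One planned summary, SAP 9.4.8, names an event that the protocol neither grades nor collects under that name, and no other SAP section supplies the by-treatment, DAIDS-graded summary of infusion-related reactions. The listing, frequency table and grading are suitable and need only the right event.

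The consequence is limited to presentation. No adverse event leaves the reporting, and no estimate or escalation decision is shown to change. It would be too strong to say that the SAP deliberately replaced one event with another, or that the final tables will be wrong: a mislabel is more likely, and the shells were not available. The conclusion rests on a literal reading of the SAP and on the supplied text alone.

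**What to change.** - Retitle SAP 9.4.8 *Infusion-related reactions*, refer to protocol 6.1.1.2, 8.3.6 and 8.3.8, and apply the listing, by-treatment frequency table and DAIDS grading already planned to those events.
- Name the shared infusion-related reaction/hypersensitivity form as the data source. State which of its records feed the 9.4.8 table and which feed the 9.4.7 listing, or that a record may appear in both.
- Delete ISR or define it in SAP section 2, and align the table shell if it carries the same label.
- If local site reactions are truly intended, state their data source and add a separate infusion-related reaction summary.

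For infusion-related reactions this costs SAP wording and possibly one relabelled shell. It needs no new data collection, since the protocol already provides for collecting and grading these events.

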9.4.9 Severe acute respiratory syndrome coronavirus 2 (SARS-CoV-2) infection

Data from SARS-CoV-2 clinical screening, serology, and point-of-care test will be listed, if available.

9.4.10 Other assessments

All other safety assessments not detailed in this section will be listed but not summarized or statistically analyzed.

9.4.11 Safety and Tolerability Statistical Methodology

No inferential statistical analyses are planned.

10. INTERIM ANALYSES

No interim statistical analyses are planned.

11. CHANGES FROM THE PROTOCOL SPECIFIED STATISTICAL ANALYSES

There were no changes from the protocol specified statistical analyses.

13. DATA PRESENTATION

13.1 Derived Parameters

Individual derived parameters (e.g. PK parameters) and appropriate summary statistics will be reported to three significant figures. Observed concentration data, e.g. C_{max} , should be reported as received. Observed time data, e.g. t_{max} , should be reported as received. N and percentage values should be reported as whole numbers. Median values should be treated as an observed parameter and reported to the same number of decimal places as minimum and maximum values.

13.2 Missing Data

Missing data will not be displayed in listings.

13.3 Insufficient Data for Presentation

Some of the TFLs may not have sufficient numbers of subjects or data for presentation. If this occurs, the blank TFL shell will be presented with a message printed in the center of the table, such as, "No serious adverse events occurred for this study.".

